5.0 DOSING DELAYS/DOSE MODIFICATIONS

Dose Modification of Pacritinib within Patients

The dose of Pacritinib will be adjusted according to the guidelines shown in the following tables for study drug-related and **clinically significant** toxicity. If toxicity is not covered in the table, doses may be reduced or held at the discretion of the investigator for the patient's safety and documented in the patient's medical record.

Patients with study-drug related toxicities that are manageable with supportive therapy may not require dose reductions.

Table 4. Pacritinib dose de-escalation

Clinically significant non-hematologic treatment related toxicity and dose management	
Toxicity Grade	Management/Action
1 or 2	No change required. If the toxicity persists at Grade 1 or 2, then reduction to a lower dose level is allowed according to Investigator judgment and the likelihood that the toxicity is related to Pacritinib.
3	Hold treatment. Treatment may resume if toxicity is resolved to Grade \leq 1 or returned to baseline. If the toxicity resolves within 7 days, Pacritinib may be resumed at the same level or at the next lower dose level at the discretion of the Investigator. Toxicity lasting more than 7 days will require dose reduction to the next lower dose level.
4	Hold treatment. Treatment may resume if toxicity is resolved to Grade \leq 1 or returned to baseline at the discretion of the Investigator. Treatment will be reduced by two dose levels from the level at which the toxicity was observed. If Grade 4 toxicity occurs at 200 mg/d, the patient should be discontinued from the study.

Table 5. Dose reduction levels

Starting dose level	400 mg/d
Dose level -1	300 mg/d
Dose level -2	200 mg/d

Patients that require reduction of more than 2 dose levels will be removed from the study.

Part 2 Dose Schedule

The pacritinib dose will be decreased to 200 mg in AM and 100 mg in the evening for the first cycle of combined therapy. The dose may be reduced further to 100 mg in AM and 100 mg in PM if grade 2 non-hematopoietic toxicity is observed. Pacritinib will be held for up to 14 days if grade 3 non-hematopoietic toxicity is observed and then restarted at 100 mg BID (every 12 hours). If no toxicity is observed in the first cycle of combined therapy, the pacritinib dose may be increased to 200 mg BID (every 12 hours) on subsequent cycles of combined therapy.

Patients with drug-related toxicities that are manageable with supportive therapy may not require dose reductions. Otherwise, the following dose adjustment rules apply:

Table 6:

Clinically significant treatment related toxicity and dose management
--

NCI CTCAE Grade	Management/Action
0-2 non-hematologic toxicity	No dose reduction. Grade 2 toxicities that are persistent and intolerable (i.e. stomatitis) can result in dose delays or dose reductions to the next lower dose level.
3-4 clinically significant non-hematologic toxicity	Hold until recovery to NCI CTCAE grade 0-1. If recovery occurs within 2 weeks after treatment has been held, dose should be reduced to -1 dose level, if appropriate.

Table 7: Suggested dose reductions for azacitadine and decitabine*

Dose Level	Decitabine (in mg/m ² for 5 days)	Azacitadine (in mg/m ² for 7 days)
0	20	75
-1	15	50
-2	10	25
-3	10 for 4 days	25 for 5 days

*Dose reductions different than those described above are acceptable after discussion with the investigator, and require documentation of the rationale for such action in the patient's medical record.

Study cycles should be administered every 28 days \pm 5 days or upon resolution of any clinically significant study drug related AE to grade 0-1, whichever occurs first. Subsequent cycles will begin on the first day of Decitabine or Azacitidine therapy, and in the absence of toxicity, Pacritinib administration will not be interrupted. If a subsequent cycle is delayed due to adverse events related to HMA-agent, or if it is considered in the best interest of the patient to delay administration of HMA, administration of the Pacritinib may continue as planned.

Concomitant and Excluded Therapies

Patients may not receive other investigational agents, chemotherapy, or immunotherapy for the treatment of hematologic malignancy during the study apart from azacitadine or decitabine in Part 2 as described in Section 4.0, Treatment Plan.

Patients must discontinue treatment with any potent CYP3A4 inhibitors for 1 week prior to administration of study drug. Every effort should be made to avoid CYP3A4 inducers or inhibitors throughout the course of the study. If concomitant therapy with CYP3A4 inducers or inhibitors is medically necessary and there are no available or suitable substitutes, this should be documented in the patient's medical record and extreme caution taken with their continued use during the study duration.

Patients should not receive treatment with medications with a possible or conditional risk of causing Torsades de Pointes, or those associated with prolongation of the QT interval unless medically necessary. If medically necessary, close follow up and monitoring is recommended.

All medications (other than study drug) and significant non-drug therapies administered after the patient starts treatment with study drug, with any changes in dosing must be recorded in the electronic medical record.”

Erythropoietin, granulocytic or other hematopoietic colony stimulating factors for treatment of cytopenias are discouraged. If administered, the subject will not be eligible for a hematologic improvement (HI) response assessment within 2 weeks of administration.

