4.0 TREATMENT PLAN

Study Design

This is a Phase II study to evaluate the safety and efficacy of Pacritinib for the treatment of lower-risk MDS patients. The primary efficacy endpoint is the overall response rate (ORR) based on the IWG-2006 criteria, which includes complete remission (CR), partial remission (PR), and major hematologic improvement (HI). Patient's overall response will be assessed after 1 cycle of treatment but no more than after 4 cycles of treatment; cycle length is 28 days. If no response is attained after 4 cycles of treatment or if progression occurs during therapy at any time, the patient is eligible to continue on Pacritinib therapy with the addition of hypomethylating agent therapy (HMA) [Part 2]. A maximum total of 40 evaluable patients (n=40) will be enrolled.

Agent Administration

All patients will be registered through Protocol Data Management System (PDMS) or CORE.

One initial schedule of Pacritinib will be studied: 200 mg orally twice daily (every 12 hours) without regards to per oral (p.o.) intake. Study cycles will be administered every 28 days \pm 5 days or upon resolution of any clinically significant study drug related adverse event (AE) to grade 0-1, whichever occurs first.

Patients will receive the first course of therapy without interruption regardless of degree of myelosuppression unless patients with an un-transfused pre-treatment platelet count $\geq 50 \times 10^9/L$

$10^9/L$ drops to less than $10 \times 10^9/L$. In that case, drug will be held until platelets return $\geq 10 \times 10^9/L$ and resumed at the next lower dose if appropriate. If prolonged myelosuppression is observed with evidence of a hypocellular marrow (marrow cellularity less than 5% without evidence of recurrent MDS) drug will be stopped. Subsequent courses of Pacritinib will be given at the next lower dose, once counts recover. Count recovery will be considered if the ANC is $\geq 1 \times 10^9/L$ and platelets $\geq 50 \times 10^9/L$. For other clinical situations, subsequent courses of therapy will be administered at the discretion of the treating physician. Patients with residual disease may start the next cycle with neutrophil or platelet counts lower than these, if judged to be in the best interest of the patient to initiate the next cycle. The decision to treat should be documented in the patient's medical record.

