Patients will be assessed for disease response at the completion of 4 cycles of treatment. If there has been no response to therapy (i.e. stable disease per IWG-2006), or if disease progression is identified, patients will be eligible to continue on the study with the addition of 5-azacitadine or decitabine, with continuation of Pacritinib, in **Part 2** (Pacritinib + HMA). Patients responding to therapy will continue on Pacritinib monotherapy. Patients with disease progression prior to 4 cycles of Pacritinib are also eligible to initiate the Pacritinib + HMA study portion prior to the completion of 4 cycles. In these patients, disease assessment including bone marrow aspiration should be performed prior to the initiation of Part 2. Patients receiving Pacritinib + HMA will be re-assessed for disease response after 4 cycles of *combination* treatment on Part 2. Patients on pacritinib monotherapy in Part 1 who manifest disease progression at any time, including before or after completion of 4 cycles of treatment, can continue on study in Part 2 with the addition of a hypomethylating agent.

The addition of HMA should be initiated on Day 1 of the next Pacritinib treatment cycle whenever possible. HMA dosing and dosing adjustments should be performed according to the approved package insert, or at a dose of decitabine 20mg/m² IV over 1 hour for 5 days every 4 weeks and according to standard of care (see Section 5.0 for rules of dose reduction or delay).

Duration of Therapy

All patients must complete a screening visit, day 1 visits for each new cycle (+/- 5 days), end of treatment visit and whenever possible, an end of study safety visit 28 days after the last dose of Pacritinib (+/- 7 days).

Patients may remain on study for up to 12 months if the patient demonstrates clinical benefit and no excessive toxicity (i.e. no clinically significant study-drug related grade ≥ 3 toxicity). Patients who are experiencing clinical benefit beyond 12 months and have not experienced excessive toxicity may be eligible to continue therapy after discussion with the PI and the discussion documented in the patient's medical record. After the end of therapy and/or 30 days after your last dose of study drug, the study staff will follow your health status by phone call every 2 months (+/- 2 months) until you receive another cancer treatment.

Treatment is expected to continue until one of the following criteria applies:

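### Section 5.0 gives one Part 2 entry dose (300 mg/d) and does not provide for patients already reduced to 200 mg/d in Part 1, for whom it would be a 50% increase

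*Combined protocol and SAP*

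**What the plan says.** **Part 1 dose levels.** Pacritinib starts at 200 mg twice daily (Section 4.0, Agent Administration). Table 5 lists this as 400 mg/d, with level -1 at 300 mg/d and level -2 at 200 mg/d. Only patients who need more than two levels of reduction are removed from the study.

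**Routes down in Part 1.**
- Table 4, grade 3: "Toxicity lasting more than 7 days will require dose reduction to the next lower dose level".
- Table 4, grade 4: "Treatment will be reduced by two dose levels from the level at which the toxicity was observed". Discontinuation is tied to a recurrence at the bottom level: "If Grade 4 toxicity occurs at 200 mg/d, the patient should be discontinued from the study".
- Table 4 also permits a reduction for persistent grade 1 or 2 toxicity.
- Section 4.0 adds a one-level reduction for prolonged myelosuppression: "Subsequent courses of Pacritinib will be given at the next lower dose, once counts recover".

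**Entry to Part 2.** Section 4.0 makes non-responders after four cycles, and patients who progress at any time, eligible for the combination "with continuation of Pacritinib". A progressing patient "can continue on study in Part 2 with the addition of a hypomethylating agent". Neither sentence sets a condition on the pacritinib dose at that time.

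**Dose in Part 2.** Section 5.0, Part 2 Dose Schedule, gives one dose for the first combination cycle: "The pacritinib dose will be decreased to 200 mg in AM and 100 mg in the evening". A step to 100 mg twice daily is available once grade 2 or grade 3 non-hematopoietic toxicity has been seen in Part 2. For later cycles, "If no toxicity is observed in the first cycle of combined therapy, the pacritinib dose may be increased to 200 mg BID".

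**The concern.** The Part 2 schedule starts pacritinib lower than the Part 1 starting dose in the cycle that introduces a second agent, which is a sensible precaution. The rule is written as a single dose, though, and the direction of change depends on where the patient stands. A patient at 400 mg/d goes down and a patient at 300 mg/d stays put. A patient at 200 mg/d, if given the stated dose, goes up.

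That last group has tolerated pacritinib least. The Part 2 step-down to 100 mg twice daily does not protect them at entry, because it applies only after new toxicity. At stake are the safety of individual patients and consistent dosing between patients in the same situation. No error rate or primary estimate is shown to change.

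**Working it through.** **1. Reproduce the stated starting dose.** 200 mg × 2 = 400 mg/d, which agrees with Table 5.

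**2. Part 2 entry dose.** 200 mg + 100 mg = 300 mg/d.

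**3. Change on entry at each permitted Part 1 level,** (300 − current) / current:

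| Part 1 dose | Entry at 300 mg/d | Change | Lower of 300 mg/d and current dose |
|---|---|---|---|
| 400 mg/d | 300 mg/d | −25% | 300 mg/d |
| 300 mg/d | 300 mg/d | 0% | 300 mg/d |
| 200 mg/d | 300 mg/d | +50% | 200 mg/d |

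**4. Can a patient be at 200 mg/d and enter Part 2?** Yes. A grade 4 event at 400 mg/d takes the patient two levels down, to 200 mg/d, and Table 4 allows dosing to resume once the event has resolved to grade 1 or less or returned to baseline. Two one-level reductions (400 to 300 to 200 mg/d) lead to the same place. One reduction alone reaches only 300 mg/d, where the entry rule causes no change. Section 4.0 then opens Part 2 on non-response or progression, whatever the dose.

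**5. The two readings for a patient at 200 mg/d.**
- Give the stated dose: +50% in the cycle in which the HMA starts.
- Read the sentence as covering only patients above 300 mg/d: no entry dose is given. Section 4.0 says that pacritinib continues but does not say at what dose.

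**6. Can the change in exposure be sized?** The protocol reports that exposure rises less than in proportion to dose, so +50% in dose should not be taken as +50% in exposure. The available figures are these:

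| Source (Section 2.3) | Comparison | Ratio | Change |
|---|---|---|---|
| Table--9, Day 15 mean AUC0-24 | 300 vs 200 mg | 132/125 = 1.056 | +6% |
| Table--11, Day 15 mean AUC0-24 | 300 vs 200 mg | 177/153 = 1.157 | +16% |
| Table--13, single-dose AUC0-inf, doses assumed to add | 200+100 vs 100+100 mg | 240,610/185,444 = 1.297 | +30% |
| Table--9, Day 15 mean AUC0-24 | 400 vs 200 mg | 125/125 = 1.000 | 0% |
| Table--11, Day 15 mean AUC0-24 | 400 vs 200 mg | 220/153 = 1.438 | +44% |
| Table--12, Day 15 mean AUC0-24 | 400 vs 200 mg | 211/54 = 3.907 | +291% |

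For Table--13, the sums are 147,888 + 92,722 = 240,610 and 2 × 92,722 = 185,444 ng·h/mL.

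The patient figures compare different patients in cohorts of 3 to 9, dosed once daily, with wide standard deviations. The single-dose figure comes from healthy volunteers and needs an additivity assumption. The three patient studies disagree from 0% to +291% on one dose pair. These data do not yield a usable range for patients with MDS dosed twice daily.

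**7. Number affected.** The documents give neither the expected number of patients at 200 mg/d nor the number of those who would go on to Part 2. It is probably small, since it takes both a two-level reduction and non-response or progression.

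**The case against.** **An increase is not what the text orders.** The verb is to decrease. For a patient at 200 mg/d the instruction cannot be carried out, and a sensible physician would not read it as an order to escalate. This stands. A reader might infer that the protocol instructs a 50% escalation in its least tolerant patients; the wording does not support that. What remains is a gap: 300 mg/d is the only entry dose stated, and reading the sentence narrowly leaves this patient with none.

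**Discretion covers the case.** Section 4.0 leaves later courses in other clinical situations to the treating physician, and Section 5.0 lets the investigator reduce or hold the dose for toxicities outside the table. Entry to Part 2 is itself permissive, and its first cycle is given at one centre (Section 6.0). This softens the risk. It sets no entry dose, however, and the Section 5.0 clause concerns a current toxicity rather than one that has resolved.

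**Such patients may not remain on study.** Section 4.0 links remaining on study to the absence of clinically significant drug-related toxicity of grade 3 or higher, and unacceptable adverse events are grounds for stopping. That is in tension with Table 4, which expressly resumes dosing after grade 3 and 4 events. It does not bar these patients from Part 2, and reductions for persistent grade 1 or 2 toxicity fall outside it.

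**Higher dose has not meant more severe toxicity.** The summaries of the earlier studies say that increasing dose did not bring more frequent grade 3 or 4 events. The same material calls gastrointestinal toxicity dose dependent, and Table 4 uses dose reduction as the remedy. This limits the concern but does not remove it.

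**The later increase to 200 mg twice daily.** A reader might see a second defect in that step being open to patients reduced in Part 1. The documents do not support this. The step is optional and requires a first combination cycle free of toxicity. Barring it would also reach patients at 300 mg/d, whom the entry rule leaves unaffected. Whether to allow it is a clinical judgement and is not part of this point.

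**Conclusion.** The gap is real and minor. Section 5.0 provides no safe, unambiguous Part 2 entry dose for a patient already at 200 mg/d: the one dose stated is +50% for that patient, and the narrower reading states none. This rests on the text of Tables 4 and 5, the Part 2 entry provisions of Section 4.0 and simple dose arithmetic, with no outside assumption.

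Three things are not claimed. An increase was probably not intended. The change in exposure cannot be reliably sized. No distortion of the Table 14 toxicity count can be shown: a reader might infer that extra grade 3 or 4 events would push Part 2 towards its stopping boundary, but the documents give neither the number of patients nor a dose-toxicity relation from which to estimate it. The judgement that few patients are affected is an assumption, since the documents set no bound.

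**What to change.** Add one sentence to Section 5.0, Part 2 Dose Schedule: the pacritinib dose in the first cycle of combined therapy is the lower of 300 mg/d and the patient's current Part 1 dose.

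Entry doses for patients at 400 mg/d (to 300 mg/d) and at 300 mg/d (unchanged) stay as they are. A patient at 200 mg/d would enter at 200 mg/d. The cost is slightly lower pacritinib exposure in those few patients, 200 instead of 300 mg/d in that cycle. Sample size, stopping boundaries and analysis need no change.

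### In Part 2 the rules for pacritinib after grade 3 toxicity give opposite instructions for a patient not recovered at day 14, and the dose after grade 4 is ambiguous

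*Combined protocol and SAP*

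**What the plan says.** All the relevant text is in Section 5.0, apart from a 6-week limit on interruption of study drug in Sections 4.0 and 11.0.

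- **Opening of Section 5.0.** "The dose of Pacritinib will be adjusted according to the guidelines shown in the following tables". Nothing here limits Table 4 to Part 1.
- **Table 4, grades 3 and 4.** Treatment is held. "Treatment may resume if toxicity is resolved to Grade" 1 or lower, or has returned to baseline. After grade 4, "Treatment will be reduced by two dose levels from the level at which the toxicity was observed", and "If Grade 4 toxicity occurs at 200 mg/d, the patient should be discontinued from the study".
- **Table 5.** The levels are 400 (start), 300 (level -1) and 200 mg/d (level -2). Below the table: "Patients that require reduction of more than 2 dose levels will be removed from the study".
- **Part 2 Dose Schedule, text.** "The pacritinib dose will be decreased to 200 mg in AM and 100 mg in the evening for the first cycle of combined therapy". After grade 3: "Pacritinib will be held for up to 14 days if grade 3 non-hematopoietic toxicity is observed and then restarted at 100 mg BID". If the first combined cycle passes without toxicity, "the pacritinib dose may be increased to 200 mg BID (every 12 hours) on subsequent cycles of combined therapy". The paragraph gives no action for grade 4.
- **Table 6.** It follows in the same Part 2 subsection and is introduced as the rule that otherwise applies. Grades 3 and 4 share one row: hold until grade 0-1 and, if recovery comes within 2 weeks, reduce to the -1 level if appropriate. No drug is named. Table 7, directly below, lists levels for decitabine and azacitidine.

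**The concern.** The Part 2 sentence caps the hold and directs a restart by the calendar, whereas both tables make the restart depend on recovery. Followed literally, the sentence re-exposes a patient to pacritinib 200 mg/d, alongside a hypomethylating agent, while a grade 3 event may still be active. After grade 4, two investigators could each follow a table in the protocol and give different pacritinib doses.

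These rules are likely to be used. The safety summary in Section 2.3 reports grade 3/4 gastrointestinal events in 33 of 191 pacritinib patients (17%). The Part 2 design treats therapy-related non-hematologic grade 3/4 toxicity as unacceptable only above 30%. The stake is patient safety and consistent dosing, not a statistical figure.

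**Working it through.** The plan gives no figure to reproduce. The check sets the rules side by side and converts each to mg/d.

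**Doses in use.** Part 2 cycle 1: 200 + 100 = 300 mg/d. Restart dose: 100 mg BID = 2 × 100 = 200 mg/d. Later combined cycles: up to 200 mg BID = 2 × 200 = 400 mg/d. One Table 5 step is 100 mg/d.

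**Condition for restart after grade 3**

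| Rule | Condition | Patient not recovered at day 14 |
|---|---|---|
| Part 2 text | none stated; hold of at most 14 days | restart at 200 mg/d |
| Table 6 | grade 0-1 | keep holding |
| Table 4 | grade 1 or lower, or baseline | keep holding |

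This conflict does not depend on which drug Table 6 covers. If it covers only the hypomethylating agent, Table 4 is the pacritinib table, and it also requires recovery. Table 6 gives a restart dose only for recovery within 2 weeks. For slower recovery the only stated limit is 6 weeks, which is 42 days and leaves 42 − 14 = 28 days after day 14.

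**Pacritinib dose after recovery.** Table 6 is taken here to govern pacritinib and to mean one Table 5 step down.

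| Event | Part 2 text | Table 4 | Table 6 |
|---|---|---|---|
| Grade 3 at 400 | 200 (if the sentence applies after cycle 1) | not compared | 400 − 100 = 300 |
| Grade 3 at 300 | 200 | not compared | 300 − 100 = 200 |
| Grade 4 at 400 | silent | 400 − 2 × 100 = 200 | 400 − 100 = 300 |
| Grade 4 at 300 | silent | 300 − 2 × 100 = 100, off study | 300 − 100 = 200 |
| Grade 4 at 200 | silent | discontinue | 200 − 100 = 100, no such level |

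A dose of 100 mg/d is (400 − 100)/100 = 3 levels below the Table 5 start. The rule on reductions of more than two levels therefore removes the patient.

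At 300 mg/d the text and Table 6 agree after grade 3. The differences are at 400 mg/d after either grade (200 against 300 mg/d), and at 300 mg/d after grade 4 (off study against 200 mg/d).

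**The case against.** The strongest reply is that Section 5.0 has to be read as a whole. Table 6 stands under the Part 2 heading, is introduced as the applicable rule and requires recovery. A hold of up to 14 days is variable, which fits a hold that ends on recovery. This stands in part: a reader might infer that Part 2 has no recovery condition at all, and the documents do not support that. But the sentence neither cites Table 6 nor says what happens when day 14 arrives without recovery.

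A second reply is that Tables 4 and 6 need not conflict after grade 4. If Table 6 is the specific Part 2 rule, it displaces Table 4. If it belongs with the hypomethylating agents in Table 7, Table 4 governs pacritinib. Either way one rule remains. This also stands, so a flat contradiction between the tables is not established. What is established is that the protocol states neither scope.

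Three further inferences should be resisted:

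- Reading Table 6's level as the fixed Table 5 label would leave 300 mg/d unchanged and raise 200 to 300 mg/d. That contradicts the table's own instruction to reduce the dose.
- Removal after grade 4 at 300 mg/d under Table 4 is not merely implied. It follows from the stated rule on reductions of more than two levels.
- The grade 3 restart sentence comes right after the cycle 1 dose. Applying it at 400 mg/d, which is reachable only in later cycles, is an assumption.

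There are also backstops. Table 6 leaves room for judgment, and an unacceptable adverse event is a reason to stop treatment. These lower the urgency but do not resolve the wording.

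**Conclusion.** The point holds as an inconsistency for grade 3 and an ambiguity for grade 4. The firm part is the restart condition, where the text and both tables give opposite instructions for a patient not recovered at day 14. This takes non-hematopoietic in the text and non-hematologic in the tables to mean the same thing.

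The dose differences are conditional. After grade 3 at 400 mg/d, 200 against 300 mg/d requires the sentence to reach beyond cycle 1 and Table 6 to cover pacritinib. After grade 4 at 400 mg/d, the same 200 against 300 mg/d requires both Table 4 and Table 6 to be available for pacritinib in Part 2, which the text leaves open.

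The wording should be corrected, but the backstops mean it is not a fatal flaw. A reader might infer that the toxicity monitoring or the stopping boundaries are affected. Nothing in the documents supports that.

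**What to change.** 1. Replace the Part 2 grade 3 sentence with wording to this effect: *After grade 3 non-hematologic toxicity, hold pacritinib and restart at 100 mg BID only once the event is at grade 1 or lower or back to baseline. If that has not happened by day 14, continue the hold, subject to the existing 6-week limit.*
2. State which drug or drugs Table 6 governs, and whether its -1 level means one step down in Table 5 or in Table 7. Name the single table that governs pacritinib after grade 4 in Part 2.

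Item 1 uses conditions already in the protocol. Item 2 needs a decision by the sponsor. Table 4 is the more conservative option after grade 4, but it takes patients with grade 4 toxicity at the Part 2 starting dose of 300 mg/d off study, where Table 6 may allow them to resume. The Statistical Analysis Plan counts patients who drop out before completing all cycles as failures, so that choice could affect the Part 2 response rate. The documents give no basis for estimating by how much.

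The edit itself is a few sentences and a table note in Section 5.0. Sample size, stopping boundaries and analysis methods stay as they are.
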